Rationale: **There are no major breakthroughs on the horizon in the field of pharmacotherapy or psychotherapy for the rapid treatment of depression (within one week) without any significant side effects, so this is a novel approach. Triple chronotherapy is a term used to describe a combination of total sleep deprivation, followed by advance of sleep cycle and bright light therapy. Three small RCTs suggest that this is a promising treatment for the rapid treatment of depression. In addition, depression is a heterogeneous condition and this study has the potential in a larger trial to be part of a paradigm shift to determine subtypes of depression that may determine the type of treatment offered.**

Trial Objectives and Design

Our objective is to determine the feasibility of conducting a larger randomized controlled trial (RCT) of triple chronotherapy in a community sample of patients with depression, and enable us to determine

- 1) agreement to be randomised.
- 2) whether clinicians can recruit participants.
- 3) estimates of participant flow.
- 4) the feasibility of delivering the intervention in the community.
- 5) adherence to the protocol.

Aims: To conduct a double blind RCT comparing adding triple chronotherapy to standard treatment of care. Both groups will receive standard treatment as usual (TAU).

We hypothesise that:

- 1) Triple chronotherapy (Total Sleep Deprivation, Phase Advance and Bright Light Therapy) with standard care will be more effective than the control treatment with standard care on the Hamilton Depression Rating Scale (6 item) at 1 week.
- 2) The superiority of Triple Chronotherapy over the control treatment will be maintained at follow up at 2, 4, 8 weeks and at 6 months.

3.1.1 *Primary endpoints*

Our outcome measures are

- 1) agreement to be randomised.
- 2) whether clinicians can recruit participants.
- 3) estimates of participant flow.
- 4) the feasibility of delivering the intervention in the community.
- 5) adherence to the protocol.

[figure not shown]
3.1.2 *Secondary endpoints*

We will explore the means and SDs of the 6 item Hamilton Depression Rating Scale (Bech, 1981; O'Sullivan, 1997) outcomes to help inform the power analysis for a larger RCT.

Trial Design

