This is a randomised parallel group single blind design. We will evaluate adding either Triple Chronotherapy or a control treatment to standard care. This design aims to show that we are able to recruit participants and that participants are able to adhere to the interventions. We will explore whether Triple Chronotherapy plus treatment as usual is more effective than treatment as usual on the HDRS (6 item).

Trial Flowchart

	Screen Visit	Visit 2 re-baseline before intervention	Visit 3 (1 week follow up)	Visit 4 (2 weeks follow up)	Visit 5 (4 weeks follow up)	Visit 6 (8 weeks follow up)	Visit 7 (6 month follow up)
Patient information and informed consent	X						
Intervention		X					
Outcome measures (observer rated rating scale)	X	X	X	X	X	X	X
Self-report outcome measures	X	X	X	X	X	X	X
Actigraphy and sleep diary	X		X				

4. Trial Intervention

Intervention Details

All participants who provide informed consent to participate will be randomised to receive either Triple Chronotherapy or a Control Treatment. Both groups will receive treatment as usual.

1) Triple Chronotherapy

This consists of (a) *Total Sleep Deprivation* with group support on days one and two; (b) *Phase Advance of Sleep* over 5 days and daily Light Therapy. On Day 1 (e.g. Monday), patients are supported in a group to stay up all night. We will arrange various activities to help patients stay awake accompanied by a Health Care Assistant (HCA) at the Hospital (e.g. watch a film; exercise; receive information on sleep hygiene; listen to music; short walk) and have access to coffee/ tea and snacks.

The next step is to *advance the phase of sleep*. Patients are helped to stay awake on Day 2 (Tuesday) at the hospital. They will either be collected by a relative or sent home by a taxi to go to bed at about 5pm. They should not drive or operate machinery. They wake by about 1am and will be invited to come to the hospital with support by a HCA in a group to stay awake. They will leave to go home by about 8am. They will then go to bed on Day 3 (Wednesday) at about 7.30pm. They will be asked to sleep until 3am. No further support is provided by the Hospital to stay awake at night. They then go to bed on Day 4 (Thursday) from 9.30pm to 5am and on Day 5 (Friday) at 11pm to resume a normal sleep routine waking by 6.30 to 7am. They will be given an information leaflet on sleep hygiene and given the opportunity to ask questions.

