(c) *Bright Light Therapy* is given on Day 2 onwards daily. This is provided by a Carex Day Classic Light. The time of the therapy is optimised in the morning according to the patient's pattern of sleep. A patient sits about one foot away from a bright light box, that emits 10,000 Lux. It is positioned slightly above the head and pointing downwards at 45 degrees. Patients are free to have breakfast, read or use a computer while facing towards the light. Treatment normally last 30 minutes or more and will continue for 6 months. Possible side effects in the triple chronotherapy group include tiredness after sleep deprivation. A few people may experience nausea or headache after beginning light therapy. (In healthy individuals bright light therapy was not associated with any significant difference in side effects compared to dim light therapy (Botanov, 2013). However, patients with any significant side effects may be asked to reduce the exposure time by 10 minutes. Active treatment may theoretically trigger a manic episode, but patients with bipolar disorder are excluded and so this should be rare. We will however warn the patient and carer of this rare possibility. Patients may also receive standard care.

2) Control treatment

Participants will be given information on sleep hygiene and getting a good night's sleep in a written leaflet and given the opportunity to ask questions. They are then given SomniLight Amber Light daily for 1 week. Like the Bright Light Therapy, the timing is optimised in the morning according to the patient's pattern of sleep. A patient sits about one foot away from a light box, which is positioned slightly at 45 degrees above the head and pointing downwards. Patients are free to have breakfast, read or use a computer while facing towards the light. Treatment normally last 30 minutes.

The frequency of any side effect from either group will be monitored and clinicians would continue with treatment as usual. Participants with any significant side effects will be withdrawn, but included in the analysis.

Frequency and duration of intervention

The duration of the intervention is 1 week.

Intervention records

Therapy sessions (e.g wake therapy or sleep hygiene information) will be recorded in ePJS hospital records.

Subject Compliance.

Compliance to the intervention will be monitored and documented by the Health Care Assistant.

Study adherence

Participants will be encouraged to stay up during sleep deprivation as described above.

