5.5 Concomitant Medication

A patient may be taking anti-depressant medication so long as the dose has been stable for 6 weeks and there are no plans to increase the dose or to alter the medication.

A wash out time for a patient deciding to stop anti-depressant medication and recruitment is 6 weeks. Surgery/radiotherapy is allowed after the first week of the intervention.

5. Research environment

This is a single centre trial at the South London and Maudsley NHS Foundation Trust. There are no specific site requirements. Recruitment will be from local GPs on the Clinical Research Network; Improving Access to Psychological Therapies (IAPT); clinicians on the Home Treatment Teams (secondary care) in Southwark, Lewisham, Lambeth and Croydon; through Consent for Contact on CRIS and on a dedicated website. For all settings, the intervention will be conducted at a hospital where support will be provided by a health care assistant for two nights and for one day to help patients stay awake (e.g. watch a film; exercise; short walk) and have access to coffee/ tea and snacks.

6. Selection and Withdrawal of Subjects

Inclusion Criteria

- 1) Diagnosis of Depressive Episode (ICD10 F32) or Recurrent Depressive Disorder (F33).
- 2) Minimum score of 8 or more on the Hamilton Depression Rating Scale (6 item) (Range 0-22) (Bech,1981). This represents at least moderate depression.
- 3) Age 18-65
- 4) Able to give informed consent
- 5) Women of child bearing age may be included and no methods of contraception is required to enable inclusion into the trial.

Exclusion Criteria

- 1) Current diagnosis of Seasonal Affective Disorder
- 2) Current diagnosis of anorexia nervosa or bulimia.
- 3) Current diagnosis of an obsessive compulsive or related disorder
- 4) Current diagnosis of post-traumatic stress disorder
- 5) History of schizophrenia, schizoaffective disorder or bipolar disorder
- 6) Severe cognitive impairment, dementia, intellectual disability or organic brain disorder.
- 7) History of stimulant or hallucinogenic misuse, alcohol or substance misuse or dependence in past 3 months.
- 8) Borderline Personality Disorder or other personality disorder considered to be the main problem.
- 9) Duration of depression more than 2 years.
- 10) Significant risk of suicide that requires hospitalisation.

- 11) Severe eye disease or cataracts or traumatic injury or visual impairment affecting both eyes.

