Primary Efficacy Parameter To compare the rate of recruitment and adherence to the treatments in both groups	Number of participants recruited per month Adherence to the protocol This includes the number of length of naps in the active intervention.	At Week 1 At Week 1
Secondary Efficacy Parameter To compare the effects of the following measures in both groups 1) Hamilton Depression Rating Scale 2) Clinical Global Impression and Improvement Scale (Guy, 1976) 3) Quick Inventory of Depressive Symptomatology – SR version (Triveni et al, 2004). 4) Brief Ruminative Response Scale (Topper et al, 2014). 5) Pittsburgh Sleep Index (Bysse et al, 1999) 6) Euroquol 5D (EQ5-D) (1990). 7) Wrist actigraph from GeneActiv daily for 3 days pre-randomisation and 7 days post-randomisation. 8) Sleep diary daily for 3 days pre-randomisation and 7 days post-randomisation. 9) The credibility of the intervention and expectation of whether their mood will improve rapidly (Devilly, 2000). 10) Amount of anti-depressant drugs (in mg of anti-depressant equivalents) (Hayasaka et al, 2015) or	An observer rated measure of depression An observer rated measure of global severity A subjective measure of depression A measure of ruminative style A measure of sleep disturbance A measure of quality of life A measure of the sleep/wake activity, which correlates with the gold standard of sleep physiology (polysomnography). A subjective measure of total sleep time A measure of the credibility of the intervention Any additional treatment received	Baseline, rebaseline and at 1, 2, 4, 8 weeks and 6-month post-randomisation. Baseline, rebaseline and at 1, 2, 4, 8 weeks and 6-month post-randomisation. Baseline, rebaseline and at 1, 2, 4, 8 weeks and 6-month post-randomisation. Baseline, and at 1, 2, 4, 8 weeks and 6-month post-randomisation. Baseline, and at 1, 2, 4, 8 weeks and 6-month post-randomisation. Baseline, and at 1, 2, 4, 8 weeks and 6-month post-randomisation. Baseline, and at 1 week post-randomisation. Baseline, and at 1 week post-randomisation Baseline Baseline, and at 1, 2, 4, 8 weeks and 6-month post-randomisation

benzodiazepine drugs (in mg of diazepam equivalents 11) The amount of Cognitive Behaviour Therapy or any other counselling or psychotherapy (number of hours) 12) Reported side effects at 1 week.	Any additional treatment received Any reported side effects	Baseline, and at 1, 2, 4, 8 weeks and 6-month post-randomisation At 1, 2, 4, 8 weeks and 6-month post
--	--	--

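### Adherence is a primary endpoint, but its only named source overlaps none of the four timed home sleep windows, and the actigraph and diary that could show them are not linked to it

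*Combined protocol and SAP*

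**What the plan says.** Section 3.1.1 lists "adherence to the protocol" as the fifth primary endpoint. The first row of the section 8 table turns this into a comparison between arms, "To compare the rate of recruitment and adherence to the treatments in both groups", timed at week 1. The only component it spells out belongs to one arm: "This includes the number of length of naps in the active intervention".

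On the source, section 4 (Subject Compliance) says: "Compliance to the intervention will be monitored and documented by the Health Care Assistant". Section 5 (Research environment) describes that person's presence: "support will be provided by a health care assistant for two nights and for one day to help patients stay awake". The account of triple chronotherapy in section 4 shows where the contact stops. For Day 2 it says: "They will either be collected by a relative or sent home by a taxi to go to bed at about 5pm". Patients are invited back after waking at about 1am and leave by about 8am. From Day 3 on, "No further support is provided by the Hospital to stay awake at night".

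Controls receive a sleep-hygiene leaflet and a daily amber light for one week. No Health Care Assistant is mentioned for them.

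The section 8 table places sleep recording among the secondary parameters: "Wrist actigraph from GeneActiv daily for 3 days pre-randomisation and 7 days post-randomisation", with a sleep diary over the same days. The flowchart marks both at the 1-week visit. Neither is tied to adherence there or anywhere else, and section 10 (Analysis) gives no definition, threshold or summary for adherence.

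**The concern.** The trial exists to show whether this package can be delivered and followed outside an inpatient ward. The phase advance is the part that patients must manage largely alone at home, and it is one of the three components. A source that is present only for the supported hours sees adherence where it is easiest to achieve. A favourable result from that source would say little about the home nights, and a larger trial could be planned on it.

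The comparison between arms has a further gap. No control measure of adherence is defined, and the one named component, naps, applies to the active arm only.

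**Working it through.** The plan states no adherence rate, threshold or precision, so there is no figure of its own to reproduce. The check sets the clock times in section 4 against the contact described in sections 4 and 5.

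**1. Length of each timed home sleep window (end time minus start time)**
- Day 2: about 5pm to 1am = 8 h
- Day 3: 7.30pm to 3am = 7.5 h
- Day 4: 9.30pm to 5am = 7.5 h
- Day 5: 11pm to 6.30–7am = 7.5 to 8 h

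Total: 8 + 7.5 + 7.5 + (7.5 to 8) = 30.5 to 31 h.

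**2. Overlap with described contact**
Contact runs from the Day 1 night to the departure home for a bedtime of about 5pm on Day 2, and then from about 1am to 8am that night for those who accept the invitation. The start on Day 1 is not stated. Starts between 20:00 and 23:00 were tried, and the overlap with the four windows is 0 h each time. So 0 of 4 windows are directly observed. Of the five nightly sleep targets (one wake night and four windows), only the wake night lies within described contact.

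**3. Light sessions**
Active light is daily from Day 2. The assistant could be present on the mornings of Days 2 and 3 at most, which is 2 of 6 sessions over Days 2 to 7. Section 4 also says that active light continues for 6 months. Taking that as 182 days gives 181 sessions from Day 2, and 2/181 = 1.1%. For controls, 0 of 7 daily sessions have described contact.

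**4. Would the seven-day recording cover the windows?**
The table counts the seven days from randomisation. Section 6 (Randomisation Procedure) has the intervention arranged after randomisation, and the gap is not stated. Let Day 1 fall g days after randomisation. The window that starts on Day k then ends in the early hours of calendar day g + k. It is fully recorded if g + k ≤ 7 (randomisation at 9am or 5pm gives the same answer). For k = 2 to 5:

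| Gap g (days) | Windows fully recorded |
|---|---|
| 0 to 2 | 4 |
| 3 | 3 |
| 4 | 2 |
| 5 | 1 |
| 6 or more | 0 |

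So the recordings can serve as the adherence source only if they are tied to Day 1.

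**The case against.** Several points on the other side stand.

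- A reader might infer that the Health Care Assistant cannot assess controls or home nights at all. The documents do not support that. Section 4 does not limit the role to one arm or to direct observation, so the assistant could question participants. Attendance after the 1am waking is also indirect evidence on the end of the first window. What the text supports is that no control contact and no questioning procedure are described.
- The assistant is the only source named, but is not declared to be the only one. The investigators may intend the actigraph and diary for naps. If so, the plan needs to say it.
- Sessions are also logged in the hospital record. That shows delivery, not sleep at home.
- A reader might infer that the sleep recordings are wrongly labelled as efficacy data. The heading carries little weight: adherence itself stands under a primary efficacy heading, and the secondary list also holds credibility, concomitant treatment and side effects. The contrast that matters is primary against secondary, with no link between them.
- A reader might want week-1 sleep data taken out of the comparison between arms, or a figure for how many hours the arms differ by instruction. Neither is supported. The timed schedule covers Days 1 to 5 and recording lasts seven days, so removal could discard uninstructed nights. A figure would need an assumed control sleep time that the documents do not give.

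None of this supplies a written source for adherence on the home nights.

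**Conclusion.** The concern holds in this form: adherence is a primary endpoint, and the contact described for its only named source covers 0 of 4 timed home sleep windows (30.5 to 31 h). No such contact is described for controls. Data that could show sleep timing and naps are already planned, but are not linked to the endpoint. The trial can run as written, but its adherence result would rest mainly on supervised hours.

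The window count and hours follow directly from the stated clock times. The control-arm statement rests on the plan's silence. The coverage table assumes that recording starts at randomisation, and the gap to Day 1 is unknown. The recordings do not settle light adherence, because nothing in the plan says that they capture light-box use.

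**What to change.** In section 8:

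1. Name week-1 actigraphy, with the diary as support, as the source for sleep-schedule adherence and naps.
2. Score the wake night and each timed sleep window in the protocol against a tolerance fixed before data are seen. Report the proportion of targets met, with all randomised active participants as the denominator and unrecorded nights shown as unknown.
3. Use the same recordings in controls only to check that they did not adopt the schedule. Keep the Health Care Assistant's log for on-site hours.
4. Anchor the seven-day recording to intervention Day 1.
5. Keep actigraphy and diary in the secondary list, but state that arm differences on the scheduled nights (Days 1 to 5) show delivery of the schedule, not benefit.
6. State that these data do not measure light-box use. Name a separate source for light adherence in each arm, or report it as not measured.

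In section 4, reconcile the stated one-week intervention with the six-month continuation of active light, because the two imply different periods over which adherence is counted.

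The cost is protocol wording, some scoring work and, if light use is to be measured, one small new record. Some nights will be lost to missing wear or diary entries. No treatment changes.

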5.5 Concomitant Medication

A patient may be taking anti-depressant medication so long as the dose has been stable for 6 weeks and there are no plans to increase the dose or to alter the medication.

A wash out time for a patient deciding to stop anti-depressant medication and recruitment is 6 weeks. Surgery/radiotherapy is allowed after the first week of the intervention.

5. Research environment

This is a single centre trial at the South London and Maudsley NHS Foundation Trust. There are no specific site requirements. Recruitment will be from local GPs on the Clinical Research Network; Improving Access to Psychological Therapies (IAPT); clinicians on the Home Treatment Teams (secondary care) in Southwark, Lewisham, Lambeth and Croydon; through Consent for Contact on CRIS and on a dedicated website. For all settings, the intervention will be conducted at a hospital where support will be provided by a health care assistant for two nights and for one day to help patients stay awake (e.g. watch a film; exercise; short walk) and have access to coffee/ tea and snacks.

6. Selection and Withdrawal of Subjects

Inclusion Criteria

- 1) Diagnosis of Depressive Episode (ICD10 F32) or Recurrent Depressive Disorder (F33).
- 2) Minimum score of 8 or more on the Hamilton Depression Rating Scale (6 item) (Range 0-22) (Bech,1981). This represents at least moderate depression.
- 3) Age 18-65
- 4) Able to give informed consent
- 5) Women of child bearing age may be included and no methods of contraception is required to enable inclusion into the trial.

Exclusion Criteria

- 1) Current diagnosis of Seasonal Affective Disorder
- 2) Current diagnosis of anorexia nervosa or bulimia.
- 3) Current diagnosis of an obsessive compulsive or related disorder
- 4) Current diagnosis of post-traumatic stress disorder
- 5) History of schizophrenia, schizoaffective disorder or bipolar disorder
- 6) Severe cognitive impairment, dementia, intellectual disability or organic brain disorder.
- 7) History of stimulant or hallucinogenic misuse, alcohol or substance misuse or dependence in past 3 months.
- 8) Borderline Personality Disorder or other personality disorder considered to be the main problem.
- 9) Duration of depression more than 2 years.
- 10) Significant risk of suicide that requires hospitalisation.

- 11) Severe eye disease or cataracts or traumatic injury or visual impairment affecting both eyes.
- 12) History of epilepsy, uncontrolled severe headaches, or stroke as this may lower seizure threshold through sleep deprivation.
- 13) Unstable medical condition that would make wake therapy intolerable
- 14) Untreated sleep disorder such as obstructive sleep apnoea or narcolepsy
- 15) Use of photo-sensitizing drugs.
- 16) Current night-shift work.
- 17) Non-English speaker.

If a patient meets the inclusion criteria but has withdrawal symptoms from alcohol or other substances, the patient will be re-assessed for eligibility when the patient has been abstinent for 3 months.

A patient may be taking anti-depressant medication so long as the dose has been stable for 6 weeks and there are no plans to increase the dose or to alter the medication.

Selection of Participants

Anonymised information on participants who are not randomised will be reported on according to CONSORT guidelines and will include age, gender, ethnicity, whether the patient is recruited or not recruited, the reason not eligible for trial participation, or if they are eligible but declined.

Participant identification

Participants will be identified by

- a) A member of the patient's existing clinical care team will be asked to review the identifiable personal information of patients and check whether they meet the inclusion criteria or make the initial approach to patients. This may occur at the point of their initial assessment in Improving Access to Psychological Therapies (IAPT) or on Home Treatment Teams (secondary care) in Southwark, Lewisham, Croydon and Lambeth. Within IAPT settings, this is likely to be following their initial telephone screening (if appropriate), or at their high intensity assessment appointment, where depression is indicated as the client's primary problem. GPs will be encouraged to refer direct to the study.
- b) Participants may be contacted directly under the Consent for Contact (C4C). This the Trust's patient research participation register. Patients are routinely asked for consent for contact and participation in research. This creates a registry for patients who are willing for researchers to contact them about research conducted in the Trust. Consent is recorded on the electronic notes. Researchers using C4C are required to notify the

patient's care team prior to contacting a patient, so the responsible clinician is aware their patient is being invited to take part in a research study. Researchers are also required to document any contact made with patients on the notes under 'Approaches and participation' on the consent form.

- c) Participants may also refer themselves (for example on the registry of Clinical trials or by an advertisement on the web).

Randomisation Procedure / Code Break

The method of randomisation will consist of simple randomisation based constant allocation ratio of 1:1. It will be stratified according to the season. The King's Clinical Trials Unit will provide a secure web-based randomisation service. The unit is fully registered by the UKCRC and receives support funding from NIHR. A new patient alert will be sent by email (a) to the CI (b) to a research worker (non-blinded), who will inform the patient registration by telephone and arrange the intervention.

Withdrawal of Subjects

A patient would be withdrawn from the intervention if they were to become acutely manic, psychotic or suicidal or no longer wishes to continue. The reasons for withdrawal would be recorded. Participants have the right to withdraw from the study at any time for any reason. The investigator also has the right to withdraw patients from the study drug in the event of inter-current illness, AEs, SAE's, SUSAR's, protocol violations, cure, administrative reasons or other reasons. It is understood by all concerned that an excessive rate of withdrawals can render the study uninterpretable; therefore, unnecessary withdrawal of patients should be avoided. Should a patient decide to withdraw from the study, all efforts will be made to report the reason for withdrawal as thoroughly as possible. Should a patient withdraw from the intervention efforts will be made to continue to obtain all follow-up data as per protocol, with the permission of the patient.

Expected Duration of Trial.

The trial will last 6 months from randomisation to last follow up.

7. Trial Procedures

By Visit

Describe the sequence of procedures to be performed at each visit as detailed in the time/event flowchart in section 2.3.

Laboratory Tests

None required

8. Assessment of Efficacy

Parameter	Outcome Measures	Timepoint(s) of evaluation of this outcome measure (if applicable)
Primary Efficacy Parameter To compare the rate of recruitment and adherence to the treatments in both groups	Number of participants recruited per month Adherence to the protocol This includes the number of length of naps in the active intervention.	At Week 1 At Week 1
Secondary Efficacy Parameter To compare the effects of the following measures in both groups 1) Hamilton Depression Rating Scale 2) Clinical Global Impression and Improvement Scale (Guy, 1976) 3) Quick Inventory of Depressive Symptomatology – SR version (Triveni et al, 2004). 4) Brief Ruminative Response Scale (Topper et al, 2014). 5) Pittsburgh Sleep Index (Bysse et al, 1999) 6) Euroquol 5D (EQ5-D) (1990). 7) Wrist actigraph from GeneActiv daily for 3 days pre-randomisation and 7 days post-randomisation. 8) Sleep diary daily for 3 days pre-randomisation and 7 days post-randomisation. 9) The credibility of the intervention and expectation of whether their mood will improve rapidly (Devilly, 2000). 10) Amount of anti-depressant drugs (in mg of anti-depressant equivalents) (Hayasaka et al, 2015) or	An observer rated measure of depression An observer rated measure of global severity A subjective measure of depression A measure of ruminative style A measure of sleep disturbance A measure of quality of life A measure of the sleep/wake activity, which correlates with the gold standard of sleep physiology (polysomnography). A subjective measure of total sleep time A measure of the credibility of the intervention Any additional treatment received	Baseline, rebaseline and at 1, 2, 4, 8 weeks and 6-month post-randomisation. Baseline, rebaseline and at 1, 2, 4, 8 weeks and 6-month post-randomisation. Baseline, rebaseline and at 1, 2, 4, 8 weeks and 6-month post-randomisation. Baseline, and at 1, 2, 4, 8 weeks and 6-month post-randomisation. Baseline, and at 1, 2, 4, 8 weeks and 6-month post-randomisation. Baseline, and at 1, 2, 4, 8 weeks and 6-month post-randomisation. Baseline, and at 1 week post-randomisation. Baseline, and at 1 week post-randomisation Baseline Baseline, and at 1, 2, 4, 8 weeks and 6-month post-randomisation

benzodiazepine drugs (in mg of diazepam equivalents 11) The amount of Cognitive Behaviour Therapy or any other counselling or psychotherapy (number of hours) 12) Reported side effects at 1 week.	Any additional treatment received Any reported side effects	Baseline, and at 1, 2, 4, 8 weeks and 6-month post-randomisation At 1, 2, 4, 8 weeks and 6-month post
--	--	--

Procedures for Assessing Efficacy Parameters

The procedures are questionnaire based apart from the Actigraphy. This consist of a band worn around the wrist.

9. Assessment of Safety

Specification, Timing and Recording of Safety Parameters.

Sleep Deprivation has no reported side effects apart from tiredness. For light therapy, a few people may experience nausea or headache after beginning treatment. (In healthy individuals bright light therapy was not associated with any significant difference in side effects compared to dim light therapy (Botanov, 2013). However, patients with any significant side effects may be asked to reduce the exposure time by 10 minutes. Triple Chronotherapy may theoretically trigger a manic episode, but patients with bipolar disorder are excluded and so this should be rare. We will however warn the patient and carer of this rare possibility.

Procedures for Recording and Reporting Adverse Events

Adverse Event (AE): Any untoward medical occurrence in a subject to whom a therapy has been administered including occurrences which are not necessarily caused by or related to that therapy.

Adverse Reaction (AR): Any untoward and unintended response in a subject to a therapy which is related to any duration of therapy administered to that subject.

Unexpected Adverse Reaction (UAR): An adverse reaction the nature and severity of which is not consistent with the information known about the therapy in question in the view of the investigator

Serious adverse Event (SAE), Serious Adverse Reaction (SAR) or Unexpected Serious Adverse Reaction (USAR): Any adverse event, adverse reaction or unexpected adverse reaction, respectively, that

- Results in death;
- Is life-threatening;
- Required hospitalisation or prolongation of existing hospitalisation;
- Results in persistent or significant disability or incapacity;
- Consists of a congenital anomaly or birth defect.

Reporting Responsibilities

All SARs and SUSARs (excepting those specified in this protocol as not requiring reporting) will be reported immediately by the Chief Investigator to the REC and Sponsor.

9.1.1 *Adverse events that do not require reporting*

Symptoms such as tiredness, nausea, headache as described above do not require reporting. An episode of mania may be regarded as Adverse Reaction.

Stopping Rules

The trial may be prematurely discontinued by the Sponsor or Chief Investigator on the basis of new safety information or for other reasons given by the regulatory authority or ethics committee concerned.

The trial may also be prematurely discontinued due to lack of recruitment. If the study is prematurely discontinued, active participants will be informed and no further participant data will be collected.

10. Statistics

Sample Size

N=30 equally randomized to each group is usually adequate for a feasibility study exploring the rates of recruitment and attrition (Browne, 1995). We will explore the data for an estimate of effect size to determine consistency with previous studies.

Randomisation

The method of randomisation will consist of simple randomisation based on a constant allocation ratio of 1:1. It will be stratified according to the season.

Analysis

We will explore the means and SDs of outcomes to help inform the power analysis for a larger RCT of clinical and cost effectiveness of adding triple chronotherapy in depression. Follow-up will be maximised to prevent missing data by reminding participants at each visit of the importance of collecting data. Participants will be telephoned when they do not provide follow up data. The reasons for missing data will be recorded. Missing data for the primary outcome will be handled by multiple imputation to estimate missing outcome data. The self-report depressive symptom measures will be used in the imputation process.

11. Trial Steering Committee

There is no trial Steering Committee as this is a feasibility study with no significant risks.

12. Data Monitoring Committee

There is no Data Monitoring Committee as this is a feasibility study with no significant risks.

13. Direct Access to Source Data and Documents

The Investigator(s) will permit trial-related monitoring, audits and REC review by providing the Sponsor(s), and REC direct access to source data and other documents (eg patients' case sheets, blood test reports, X-ray reports, histology reports etc).

14. Ethics & Regulatory Approvals

The trial will be conducted in compliance with the principles of the Declaration of Helsinki (1996), the principles of GCP and in accordance with all applicable regulatory requirements including but not limited to the Research Governance Framework.

This protocol and related documents will be submitted for review to XXXXXX Research Ethics Committee (REC)

The Chief Investigator will submit a final report at conclusion of the trial to the funder, the REC and the Sponsor

15. Quality Assurance

Monitoring of this trial will be to ensure compliance with Good Clinical Practice and scientific integrity will be managed by the study team. Reports will be made on progress of the trial and any violations by the research worker to the Chief Investigator and Trial Management Committee.

16. Data Handling

The Chief Investigator will act as custodian for the trial data. The following guidelines will be strictly adhered to:

Patient data will be anonymised.

- All anonymised data will be stored on a password protected computer.
- All trial data will be stored in line with the Data Protection Act.
- and archived in line with Sponsor requirements

17. Data Management

An anonymised paper and electronic CRF will be used, which will be based on the outcome measures and demographic data. Participants are asked to consent to their data being shared anonymously with other researchers. They are also asked to consent to their General Practitioner being informed of participation in the study including any necessary exchange of information between their GP and the research team.

18. Publication Policy

It is intended that the results of the study will be reported and disseminated at international conferences and in peer-reviewed scientific journals.

19. Insurance / Indemnity

Insurance and indemnity is arranged by the South London and Maudsley NHS Foundation Trust

20. Financial Aspects

Funding to conduct the trial is provided by King's Health Partners.

21. Signatures

Chief Investigator

1/7/2017

[name]

N/A

Statistician (if applicable)

Date

Print name

22. References

- Amick, H. R., Gartlehner, G., Gaynes, B. N., Forneris, C., Asher, G. N., Morgan, L. C., . . . Gaylord, S. (2015). Comparative benefits and harms of second generation antidepressants and cognitive behavioral therapies in initial treatment of major depressive disorder: systematic review and meta-analysis. *BMJ*, 351, h6019.
- Ayuso-Mateos, J. L., Vázquez-Barquero, J. L., Dowrick, C., Lehtinen, V., Dalgard, O. S., Casey, P., . . . Dunn, G. (2001). Depressive disorders in Europe: prevalence figures from the ODIN study. *The British Journal of Psychiatry*, 179(4), 308-316.
